Prior to enrolment, all patients will be asked to sign an informed consent form to document that they understood the scope of the study (including procedures, follow-up evaluations, and any potential risks involved), were allowed an opportunity to ask questions pertaining to this study and were apprised of treatment alternatives. The study is open to qualifying patients without regard to sex or race.

Sample size

In this study, the primary comparison is the effectiveness of different bone substitutes in maintaining bone volumes, therefore, the sample size calculation will be based on bone volumes. To detect a difference of 5 mm³ in bone volume changes between the two bone substitutes (standard deviation of 6.96 mm³(3)) with a two-side 5% significance level and a power of 80%, a total sample size of 80 patients will be necessary, given an anticipated dropout rate of 20%. We can contribute with 50 patients (25 per group).

Outcome measures

Primary outcome variable

Volume changes of the volume changes of the peri-implant tissues will be evaluated by taking a limited view cone-beam computed tomography (CBTC) of the area of interest at implant placement, 1 and 5 years after loading.

Secondary outcome variables

Crown/implant failure: whether it will not be possible to place the crown because of implant failure or secondary to implant failure, and replacement of the crown for any reason. Implant failure is defined as implant mobility and/or any infection dictating implant removal and any mechanical complications rendering the implant unusable (e.g. implant fracture). The stability of each individual implant will be measured by the blinded outcome assessor manually by assessing the stability of the crown using the handles of two metallic instruments at 1 and 5 years after loading.

Biological and biomechanical complications: will be recorded and reported by study group. Examples of biological complications are: fistula, peri-implantitis. Examples of biomechanical complications are fracture of the metal screws, loosening of the crown, fracture of the ceramic lining.

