All data analysis will be carried out according to a pre-established analysis plan by a dentist with expertise in statistics blinded to group allocation. Descriptive statistics will be performed using mean and standard deviation for quantitative data and frequency and percentage for qualitative data. All-important harms or unintended effects in each group will be reported. The statistical unit of the analysis will be the patient. The primary outcome variable will be volume changes between baseline and 1- and 5-year after augmentation.

For volumetric analysis, an intra-rater agreement study will be performed on the operator to test his reliability. A set of 20 volumetric changes will be evaluated twice with a two-week interval between the measurements. The operator will be considered reliable if the intraclass coefficient of correlation is greater than 0.75.

A comparison of the baseline characteristics between groups will be presented. Differences in the proportion of dichotomous outcomes (e.g. prosthesis and implant failures, complications) will be compared between the groups using a chi-square test. Mean differences between groups for continuous outcomes (e.g. peri-implant marginal bone level changes, PES scores and volumetric analysis) will be compared using an independent sample t-test for pairwise comparisons. Comparisons between each time points and the baseline measurements will be made by paired t-tests, to detect any changes in marginal peri-implant bone levels for each study group.

All statistical comparisons will be conducted at the 0.05 level of significance and estimate, standard error, 95% confidence intervals and P-value will be reported for each term of the models.

In the case of early implant failure or complication the volumetric change will be measured anyway.

The statistical analysis will be intention-to-treat and deviation from the protocol will be considered according to the randomization scheme: all participants will be included in the analysis regardless of adherence to the protocol. In any case, if large deviations from the protocol are generated, a sensitivity per-protocol analysis will be performed.

Administrative procedures and data management

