The centre is required to keep complete clinical records and study forms for all patients included in the study. Case report forms (CRFs) should be filled in at the time of data collection. Complete CRFs, and disks containing the digitized clinical pictures and radiographs should be attached to the study folder of each patient.

All data requested for this study will be collected using paper CRFs. The CRFs will be stored in a secure locked place to which only the principal investigator and the responsible for data collection will have access to. Data will also be accessible to [name] and Tecnoss for monitoring purpose at their discretion. After completion of the various follow-up points (delivery of the final crowns, 1 and 5 years after loading) copies of all the CRFs will be sent to [name] who will check the data and store them in a computer secured with a password known to him only. Data will be processed by a dentist with expertise in statistics (to be decided) under supervision of [name]. Patient identity will be protected and known only to the study participants listed in the present protocol.

Protocol amendments and violations

Amendments to this protocol may be necessary and violations to the protocol are likely to occur. Any violation of the protocol should be reported in the “Complications, protocol deviation and drop-out CRF” (APPENDIX 3). In case of problems please contact the study coordinator without delay.

Case report forms (CRFs)

- Patient informed consent form
- Patient eligibility CRF (APPENDIX 1)
- Surgical, prosthetic and follow-up CRF (APPENDIX 2)
- Complications, protocol deviation and drop-out CRF (APPENDIX 3)

REFERENCES

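### Volume change at both 1 and 5 years is primary, but neither time point is named as decisive, and the sample size covers only one comparison

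*Protocol*

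**What the plan says.** Two places in the protocol define the primary outcome, and both carry two time points.

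- **Outcome measures, Primary outcome variable:** volume change is assessed by "taking a limited view cone-beam computed tomography (CBTC) of the area of interest at implant placement, 1 and 5 years after loading".
- **Statistical analysis:** "The primary outcome variable will be volume changes between baseline and 1- and 5-year after augmentation".

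The same Statistical analysis section compares continuous outcomes between groups by independent-sample t-test and names the volumetric analysis among them. It adds: "All statistical comparisons will be conducted at the 0.05 level of significance".

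The Sample size section is written for a single comparison: "To detect a difference of 5 mm³ in bone volume changes between the two bone substitutes", "with a two-side 5% significance level and a power of 80" per cent. It gives an SD of 6.96 mm³, 20% dropout and a total of 80, and mentions neither 1 nor 5 years.

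The protocol states no order of testing, no rule requiring both results, no joint test and no adjustment. It does say: "All data analysis will be carried out according to a pre-established analysis plan". That plan is not at hand, and the protocol does not say that it fixes the primary time point.

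**The concern.** There are two primary comparisons, but the error rate and power are set for one. What the 5% and the 80% mean depends on a rule that is not given.

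- If significance at either time point counts as success, the primary false-positive rate exceeds 5%.
- If both are required, the error is controlled, but power is below the planned level.
- If the two results disagree, nothing says which one answers the primary question. The trial compares a partly with a fully resorbable material, so a group difference that changes between 1 and 5 years is plausible.

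Timing adds a lesser worry. Under Administrative procedures and data management, "After completion of the various follow-up points (delivery of the final crowns, 1 and 5 years after loading) copies of all the CRFs" are sent in for checking and storage. The 1-year material is therefore handled about four years before 5-year data exist, and a choice left open could be made when 1-year results are known.

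**Working it through.** **Inputs from the protocol.** Difference 5 mm³, SD 6.96 mm³, two-sided alpha 0.05, power 80%, dropout 20%, total 80 (Sample size); independent-sample t-test, every comparison at 0.05, two time points (Statistical analysis).

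**Input not in the protocol.** The correlation ρ between a patient's 1-year and 5-year volume changes, assumed here from 0 to 0.95. Both changes subtract the same baseline CBCT, so a positive value is likely. As a guide, suppose the three scans have equal variance σ² and equal pairwise correlation r. The covariance of the two changes is then (1 − r)σ² and each variance is 2(1 − r)σ², so ρ = 0.5. If the 1- and 5-year scans resemble each other more than either resembles baseline, ρ is higher.

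**Step 1: reproduce the sample size.** The standardised difference is 5/6.96 = 0.718. For a two-sided 5% t-test, 31 per group gives 79.5% power and 32 per group gives 80.8%. So 32 per group, or 64 evaluable, are needed, and 64/(1 − 0.20) = 80. The stated total is reproduced exactly, as a calculation for one comparison.

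**Step 2: either time point counts.** With no true difference at either time, the false-positive rate is 1 − P(|Z₁| < 1.96 and |Z₂| < 1.96), where Z₁ and Z₂ are bivariate normal with correlation ρ. At ρ = 0 this is 1 − 0.95² = 9.75%, which is the maximum over all correlations for jointly normal statistics.

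**Step 3: both required.** The false-positive rate cannot exceed 5%, because each test is at 5%. With no difference at either time it is 0.25% at ρ = 0, 0.9% at 0.5 and 3.5% at 0.95. Joint power was simulated (400,000 trials per value of ρ) with 32 per group and the planned difference and SD assumed at both times.

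| Assumed ρ | Either counts: false-positive rate | Both required: joint power |
|---|---|---|
| 0 | 9.75% | 65% |
| 0.5 | 9.1% | 70% |
| 0.8 | 7.8% | 74% |
| 0.9 | 7.0% | 76% |
| 0.95 | 6.5% | 77% |

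The single-comparison reference is 5% error and 80.8% power. Neither rule reproduces both planned figures at any correlation in the table.

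**Step 4: time origin.** The outcome section counts years from loading, and the Statistical analysis section counts them from augmentation. Implants placed below 35 Ncm stay submerged and unloaded for 4 months, so for them the two origins differ by at least that long. This is not a multiplicity problem, but a named primary time point needs one origin.

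**The case against.** The strongest reply is that testing order and the handling of discordant results usually sit in the analysis plan, which the protocol cites and which is not shown. Nothing in the protocol says that either result alone would count as success. Testing everything at 0.05 also fits a fixed order, a both-required rule, or two separate questions reported with confidence intervals. This is right as far as it goes: the inflation is conditional and the detailed procedure may be elsewhere. It does not settle the point, because the protocol itself defines the primary outcome, the alpha and the sample size, and these three statements do not fit together. An unseen plan could resolve the conflict, but the protocol text would still contain it.

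Three narrower objections have some force.

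- The 9.75% figure needs zero correlation, which is unlikely with a shared baseline. About 6.5% to 9% is the more realistic range.
- Step 3 applies the full 20% dropout already at 1 year. If 38 per group were evaluable at 1 year and 32 at 5 years, joint power would be about 74% at ρ = 0.5 and 78% at 0.9. The protocol gives no dropout by visit, so the 38 is an assumption. The loss is smaller but does not vanish.
- Sending in forms is not the same as knowing a 1-year treatment effect. The volumetric assessor and the analyst are both blinded. The concern about a data-driven choice is therefore a possibility only, and the conclusion does not depend on it.

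**Conclusion.** The point holds. The protocol has two co-listed primary comparisons and a sample size for one, and does not identify which comparison the 5% error and 80% power describe. Over assumed correlations of 0.5 to 0.95, an either-counts rule would give a false-positive rate of 9.1% to 6.5% (upper limit 9.75% at zero correlation). A both-required rule would give joint power of about 70% to 77%, if the planned difference holds at both times and 32 per group are evaluable at each. The error inflation depends on a rule that the text leaves open. The missing ranking, and the lack of an answer if the time points disagree, do not depend on it. The sample size arithmetic is sound and stands once it is tied to one time point.

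**What to change.** In the Statistical analysis section, and in the primary outcome and sample size text:

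1. Name one time point, 1 or 5 years at the sponsor's choice, as the single primary comparison at two-sided 0.05, and state that the sample size refers to it.
2. State one time origin, loading or augmentation, and use it throughout.
3. Test the other time point at 0.05 as confirmatory only if the first is significant. Otherwise report it as an estimate with its 95% confidence interval.
4. Settle this before any 1-year volume data are seen, and make the pre-established analysis plan agree.

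The cost is two or three sentences. The total of 80 is unchanged and alpha is not split. The second time point loses its stand-alone primary status.

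There are two alternatives. A declared both-required rule needs no alpha correction but accepts the power shown above. Keeping an either-counts rule with 0.025 per test would need 39 evaluable per group, so 78/0.8 = 97.5, or 98 patients in total. With 64 evaluable, power per test would fall to 71.7%.

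### Does a chi-square test for implant failures and complications mislead when so few events are expected?

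*Protocol*

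**What the plan says.** The Statistical analysis section of the protocol gives one method for every binary outcome: "Differences in the proportion of dichotomous outcomes (e.g. prosthesis and implant failures, complications) will be compared between the groups using a chi-square test". It adds: "All statistical comparisons will be conducted at the 0.05 level of significance". It does not say whether the chi-square statistic is continuity-corrected, and it names no alternative for sparse tables. The patient is the unit of analysis and each patient provides one implant site, so the data form a plain 2×2 table. The same section asks for estimates and 95% confidence intervals beside P-values, asks for harms to be reported by group, and refers to a pre-established analysis plan, which is not at hand.

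Under Sample size the trial needs 80 patients in all: "a total sample size of 80 patients will be necessary, given an anticipated dropout rate of 20" per cent. It then says: "We can contribute with 50 patients (25 per group"). The groups therefore hold 40 patients if allocation is 1:1 across the whole trial, or 25 if this centre is analysed alone.

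The binary outcomes are listed as secondary. For failure: "Implant failure is defined as implant mobility and/or any infection dictating implant removal and any mechanical complications rendering the implant unusable". Crown replacement for any reason is counted too, and biological and biomechanical complications are recorded over follow-up to 5 years. No expected rate is given for any of them.

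**The concern.** The chi-square test rests on a large-sample approximation, usually accepted when every expected count is at least 5. In a trial this small, with one implant per patient, failures may be too few to meet that rule. Some sparse tables do look alarming. Four failures against none reaches p < 0.05 by the uncorrected chi-square, while Fisher's exact test gives about 0.11. Given exactly four events and no true difference, the uncorrected test rejects 11% of the time. If that were typical of the planned analysis, one bone substitute could be reported as failing more often on evidence too weak to support it, and failure and harm are the outcomes where such a statement would be noticed.

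**Working it through.** **Inputs.** From Sample size: 25 per group (this centre) or 40 per group (80 in total at 1:1), two-sided 5% level. From Statistical analysis: chi-square test, 0.05 level. Event rates are not given, so 2%, 5%, 10% and 20% are assumed as a range.

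**The plan's own figure.** A difference of 5 mm³ with SD 6.96 mm³ gives, by the normal formula, 2 × (1.960 + 0.842)² × (6.96/5)² = 30.4, so 31 per group. The t-based calculation gives 32 per group, and 64/0.8 = 80, as stated. This concerns the primary outcome only. The protocol has no power figure for the binary outcomes.

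**Expected counts.** With equal groups the expected number of events per group is half the total, so it is below 5 until 10 events occur. That is 10/50 = 20% of patients, or 10/80 = 12.5%. This part of the concern is correct.

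**Single tables.** For 4 v 0 at 25 per group, the uncorrected statistic is 50 × (4×25 − 0×21)² / (25×25×4×46) = 500,000/115,000 = 4.35, p = 0.037. With Yates' correction it is 50 × (100 − 25)² / 115,000 = 2.45, p = 0.118.

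| Table | Per group | Uncorrected | Yates | Fisher | Boschloo | Barnard |
|---|---|---|---|---|---|---|
| 4 v 0 | 25 | 0.037 | 0.118 | 0.110 | 0.065 | 0.041 |
| 4 v 0 | 40 | 0.040 | 0.124 | 0.116 | 0.082 | 0.043 |
| 6 v 1 | 25 | 0.042 | 0.103 | 0.098 | 0.065 | 0.053 |
| 6 v 1 | 40 | 0.048 | 0.114 | 0.108 | 0.070 | 0.059 |

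Valid exact tests disagree on 4 v 0: Barnard's unconditional test is below 0.05, Fisher's and Boschloo's are not. For 6 v 1 all three exact tests stay above 0.05, Barnard's only just.

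**Where the 11% comes from.** Given four events at 25 per group, the chance that all fall in one group is 2 × C(25,4)/C(50,4) = 25,300/230,300 = 0.110. With seven events the corresponding rejection probability is 0.098. With two or three events it is zero, with six 0.022 and with nine 0.023. The design does not fix the event total, so the error rate of the planned analysis is the average over totals.

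**Actual false-positive rate.** The two binomial distributions were enumerated in full, with the same event rate in both groups:

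| Event rate | Uncorrected, 25 | Fisher, 25 | Uncorrected, 40 | Fisher, 40 |
|---|---|---|---|---|
| 2% | 0.2% | 0.0% | 0.7% | 0.0% |
| 5% | 2.0% | 0.1% | 4.3% | 0.4% |
| 10% | 4.9% | 0.9% | 5.9% | 1.7% |
| 20% | 5.5% | 2.2% | 5.1% | 2.8% |

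Wherever fewer than 10 events are expected, the maximum for the uncorrected test is 5.5% (25 per group) and 5.9% (40 per group).

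**What an exact test would cost.** For true rates of 2% and 20% at 25 per group, power is 59% for the uncorrected chi-square, 43% for Boschloo's test and 30% for Fisher's.

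**The case for a change.** The best argument for a change does not rest on 4 v 0. It is that 6 v 1 is significant by the uncorrected chi-square at both trial sizes and by none of the three exact tests, and that the verdict on 4 v 0 moves from about 0.04 to about 0.12 according to a correction the protocol does not mention. The analyst has yet to be named, the outcomes describe failure and harm, and one sentence would settle the matter.

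The facts in this argument stand. Their weight is small. The 6 v 1 table misses 0.05 by Barnard's test by 0.003 to 0.009, which is the same excess as the 5.5% to 5.9% peak error and no more. The choice of version is a real gap, but either way of filling it is defensible: the uncorrected test holds its level closely, while Yates' correction or a switch to Fisher's test errs towards caution. A continuity or small-count rule is ordinary content for the analysis plan to which the protocol refers.

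The one-sentence change also has a cost. For harms in a small trial, halving the power to see a tenfold difference in rates is a poor exchange for removing an excess error of at most about one percentage point. Boschloo's test softens the loss but does not remove it.

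**Conclusion.** No change to the protocol is needed. The rule of thumb on expected counts would be broken with fewer than 10 events, but breaking it does not make this analysis anticonservative in any way that matters: the false-positive rate is at most about 6% in that range, and below 5% at event rates up to 5%. The high figures of 10% to 11% belong to particular event totals. Exact tests trade power for caution, so preferring one is a choice rather than a correction.

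What is left is that the version of the chi-square test and any small-count rule are unstated, which can decide the label on an isolated table such as 4 v 0. This touches secondary outcomes only. The primary volume comparison and the sample size are unaffected, and the required estimates and confidence intervals mean that readers need not depend on one P-value.

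The conclusion assumes equal groups of 25 to 40 and event rates between 2% and 20%. The protocol gives no rates. Implant failure is plausibly rare, whereas complications and crown replacement over 5 years could reach 10 events, in which case the concern about expected counts would not arise for them.

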Peri-implant marginal bone level changes: periapical digital radiographs will be made with the paralleling technique at implant placement, at 1 and 5 years of loading. In case of an unreadable radiograph, the radiograph must be made again. Peri-implant marginal bone levels will be measured using the Image J (National Institutes of Health, Bethesda, Maryland, USA) software. The software will be calibrated for every single image using the known implant length or, if the full implants is not visible on the radiograph, the implant diameter. Measurements of the mesial and distal bone crest level adjacent to each implant will be made to the nearest 0.01 mm. Reference points for the linear measurements will be: the coronal margin of the implant collar and the most coronal point of bone-to-implant contact. Bone levels will be measured at both mesial and distal sides and averaged. Bone level at single implants will be averaged at group level.

Aesthetic evaluation of the clinical pictures taken at delivery of the final crown (baseline), at 1- and 5-year follow-ups, on a computer screen by an independent blinded dentist. The pictures of the vestibular and occlusal aspects must include the two adjacent teeth. The aesthetic evaluation will be done following the pink aesthetic score (4).

Materials

Bone substitutes: the non-resorbable bone substitute is composed by porcine bone granules of cortical bone (Apatos Cortical®, OsteoBiol®, Tecnoss®, Giaveno, Italy) that will be stabilized by a thermogelling synthetic copolymer with type I and III collagen gel (TSV Gel®, OsteoBiol®, Tecnoss®). The resorbable bone substitute is composed by collagenated heterologous cortico-

cancellous porcine bone mix + TSV Gel (GTO®, OsteoBiol®, Tecnoss®). No other grafting material can be used.

- Implant types:

CM Alvim (Neodent, Straumann, Basel, Switzerland) tapered cylindrical threaded bone level implants with cone-morse connection. The implant is made of titanium grade 4 cold-worked and its surface was roughened using sandblasting and acid etching (NeoPoros surface). The operator will be free to choose implant lengths (8.0, 10.0, 11.5 and 13 mm long) and diameters (3.5 and 4.3 mm) according to clinical indications and his preferences.

- Definitive crowns: Screw-retained metal-ceramic crowns.

Clinical procedures

Screening visit (APPENDIX 1)

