The choice of the implant diameter and length will be recorded. Implants will be placed slightly subcrestally, about 2 mm below the most apical bone peak, and slightly palatally. Cover screws will be placed. If there is sufficient buccal wall (no more than 4 mm of bone loss and the gap between the buccal wall and the implant is of at least 2 mm, the patient will be finally included in the study.

Disclosure of the randomised allocation

Once the implant has been placed and whether there is sufficient buccal bone (no more than 4 mm of buccal bone loss using the highest peak of palatal wall as reference point) and in the presence of an implant to buccal bone gap of at least 2 mm, the operator will know whether the bone to implant gap will be filled with a semi- or a fully-degradable bone substitute by opening the corresponding sealed envelope. It is absolutely forbidden to open the envelope containing the random code before. The surgeon will write on the Surgical and prosthetic CRF (APPENDIX 2) the patient sequential number contained in the envelope and to which of the two groups the patient is allocated.

Any residual gap between the implant surface and the socket walls will be filled with the bone substitute type as decided by the random allocation procedure. No other type of bone grafting material is allowed. Baseline periapical and limited view CBCT radiographs must be taken. If peri-implant marginal bone levels are difficult to be assessed, a second periapical radiograph will be taken. Implants achieving a torque of at least 35 Ncm will be loaded immediately while those implants placed with less than 35 Ncm will be covered with a standard (0.5 mm thick) collagen membrane of equine pericardium origin (Evolution®, OsteoBiol®, Tecnooss®) and submerged unloaded for 4 months. After 4 months they will be rehabilitated following the same procedures as all other study implants.

Post-surgical instructions and follow-ups

- Postoperative antibiotics will be prescribed: Amoxicillin 1 g 3 times a day for 6 days. Patients allergic to penicillin will be prescribed clindamycin 300 mg thrice a day for 6 days.
- Ibuprofen 400 mg will be prescribed to be taken 2 to 4 times per day, but patients will be instructed not to take it in absence of pain.
- Chlorhexidine mouthwash 0.2% for 1 minute twice a day for 2 weeks.

Prosthetic procedures

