An impression with the pick-up impression copings will be made with a polyether material. Within 2 weeks, a definitive metal-ceramic screw-retained crown will be delivered on definitive titanium abutments.

- Periapical radiographs must be made. If the peri-implant marginal bone levels are not readable a second radiograph must be taken.
- Buccal and occlusal pictures of the implant including one adjacent tooth per side must be made.

1 year after loading (APPENDIX 2):

- Crowns will be manually tested for stability.
- Periapical radiographs must be made. If the peri-implant marginal bone levels are not readable a second radiograph must be taken.
- Buccal and occlusal pictures of the implant including one adjacent tooth per side must be made.
- A limited view CBCT of the study implant must be taken.

5 years after loading (APPENDIX 2):

- Crowns will be manually tested for stability.
- Periapical radiographs must be made. If the peri-implant marginal bone levels are not readable a second radiograph must be taken.
- Buccal and occlusal pictures of the implant including 1 adjacent tooth per side must be made.
- A limited view CBCT of the study implant must be taken.

All patients will be recalled every 6 months for professional maintenance. If necessary, the number of maintenance visits can be increased.

In case of suspected implant loss, peri-implantitis, fistula, etc., observed during any of the scheduled visit or during an emergency visit, intraoral radiographs and clinical pictures must be taken and the “Complications, protocol deviation and drop-out CRF” (APPENDIX 3) should be filled in.

Time

Day 1	photos/extraction/implant placement/patient inclusion/photos/group allocation/augmentation/impression/rx/CBCT
Within week 2	definitive crown delivery/photos
1 year after loading	implant stability/impressions/rx/CBCT/photos/maintenance
5 years after loading	implant stability/impressions/rx/CBCT/photos/maintenance

Drop-outs

All drop-outs should be reported and the reason for dropping out should be investigated and reported per study group. No included patient can be excluded for any reasons by the clinical investigators.

Statistical analysis

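### The t-test on marginal bone level change is valid but does not adjust for each implant's measured baseline level; a baseline-adjusted model is a cheap, low-severity improvement of uncertain gain

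*Protocol*

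**What the plan says.** Under Secondary outcome variables, the protocol states that "periapical digital radiographs will be made with the paralleling technique at implant placement, at 1 and 5 years of loading". The level is the distance between "the coronal margin of the implant collar and the most coronal point of bone-to-implant contact", and "Bone levels will be measured at both mesial and distal sides and averaged". Each implant, and so each patient, therefore has one baseline value and one value at each follow-up.

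Under Statistical analysis, the sentence that begins "Mean differences between groups for continuous outcomes (e.g. peri-implant marginal bone level changes, PES scores and volumetric analysis" goes on to say that these "will be compared using an independent sample t-test for pairwise comparisons". No covariate is named. Apart from forming the change, the baseline level is used only within each group: "Comparisons between each time points and the baseline measurements will be made by paired t-tests". Baseline characteristics are to be compared and presented by group, but no adjustment for them is stated. The section also promises estimates for model terms without specifying a model.

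Two passages bear on what the baseline reading represents. Under Disclosure of the randomised allocation, "Any residual gap between the implant surface and the socket walls will be filled with the bone substitute type" that was allocated, and the baseline films come after that. The Time table gives the same order for day 1: "group allocation/augmentation/impression/rx/CBCT".

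**The concern.** Comparing changes by a t-test amounts to regressing the follow-up level on arm with the baseline coefficient forced to 1. That is the most precise choice only if the true slope of follow-up on baseline is 1. Measurement error in a single radiographic reading is enough to pull the slope below 1, and so is any tendency for unusual starting levels to move back towards the average.

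When the slope is not 1, two things follow. The confidence interval for the arm difference may be wider than it need be. And a difference in starting level between the arms passes in part into the estimated effect. The arms are small enough for such a difference to be appreciable.

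At stake is the precision of one secondary outcome. The primary volume comparison and the sample size are untouched.

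**Working it through.** **The plan's own figure.** The Sample size section gives 80 patients, based on volume: difference 5 mm³, SD 6.96 mm³, two-sided 5%, power 80%, dropout 20%.
- Normal approximation: 2 × (1.96 + 0.8416)² × (6.96/5)² = 30.4, so 31 per arm; 31/0.8 = 38.75, so 39 per arm and 78 in total.
- t-test: 31.4, so 32 per arm; 32/0.8 = 40 per arm and 80 in total.

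The stated 80 reproduces. It does not depend on the present point. It does give the numbers analysed: 32 per arm in the whole trial, and 25 × 0.8 = 20 per arm from the 50 patients this centre can contribute.

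**Inputs for bone level.** The protocol gives neither an SD nor a correlation. Let k = baseline SD / follow-up SD and ρ = the correlation between the two readings. Both are assumptions.

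**Formulas** (follow-up variance set to 1):
- Change score, variance per patient: 1 + k² − 2ρk.
- ANCOVA, residual variance per patient: 1 − ρ².
- Ratio ANCOVA / change score: (1 − ρ²)/(1 + k² − 2ρk). With k = 1 this is (1 + ρ)/2.
- True slope: ρ/k. Shift of the change-score estimate per unit of baseline difference: ρ/k − 1.

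**Variance ratio, ANCOVA / change score (large-sample):**

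| k | ρ = 0.2 | ρ = 0.3 | ρ = 0.5 | ρ = 0.7 |
|---|---|---|---|---|
| 1 | 0.60 | 0.65 | 0.75 | 0.85 |
| 0.75 | 0.76 | 0.82 | 0.92 | 0.995 |
| 0.5 | 0.91 | 0.96 | 1.00 | 0.93 |
| 0.3 | 0.99 | 1.00 | 0.95 | 0.76 |

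With equal SDs, the reduction is 40%, 25% and 15% at ρ = 0.2, 0.5 and 0.7. The standard error then falls by 23%, 13% and 8% (square roots 0.775, 0.866, 0.922). The gain is nil wherever ρ = k, because the slope is then exactly 1.

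**Cost of estimating the slope.** This multiplies the ANCOVA variance by about 1 + 1/(2m − 4) with m per arm: 1 + 1/60 = 1.017 at 32 and 1 + 1/36 = 1.028 at 20. Simulation agrees. Where ρ = k, the ratio was 1.016 to 1.018 at 32 per arm and 1.027 to 1.029 at 20 per arm. With k = 1 and 20 per arm, simulated ratios were 0.665, 0.777 and 0.877 at ρ = 0.3, 0.5 and 0.7, so most of the gain survives in that setting.

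**Baseline difference between arms.** If it arises by chance alone, its 95% range is ±1.96 × √(2/m) baseline SDs: 0.62 at m = 20, 0.55 at 25 and 0.49 at 32. With k = 1 and ρ = 0.5, the shift is −0.5 per unit, so a difference at that limit moves the change-score estimate by about 0.31, 0.28 or 0.25 SD. The corresponding shift for ANCOVA is about 0.

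**Validity.** Averaged over simulated randomisations, the mean error of the change-score estimate was about 0. The loss is in precision, and in bias conditional on the imbalance that happens to occur.

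**The case against.** The strongest reply is that nothing here is an error. A t-test on change is a standard, valid test, and the outcome is secondary. That stands, and it sets the severity. A reader might infer that the planned test is biased, or that it ignores the baseline altogether. The protocol supports neither reading: randomisation protects the test, and the change score subtracts the baseline in full.

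Second, the larger gains need baseline levels to vary as much as follow-up levels. The Operative procedures place implants about 2 mm subcrestally, levels are read mesially and distally whereas the gap criterion is buccal, and residual gaps are filled before the baseline film. All of this could put first contact near the collar with little spread, so that k is small. This also stands. It would be too strong to say that adjustment always helps: where ρ is close to k, it costs about 2–3% of variance at these sample sizes. Nor does the protocol give any figure for how much bone level an individual implant could gain.

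Third, the baseline film follows allocation and grafting, so a baseline difference between arms may not be chance. The caution is right, but it does not favour the present plan. If the material shifts the baseline reading by δ, the change score carries −δ in full. ANCOVA carries −βδ, which is smaller in size whenever the slope β lies between 0 and 1. Showing both results covers the point.

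Last, the protocol refers to an analysis plan fixed in advance, which might add adjustment. But the t-test is already stated in the protocol, so the proposal changes a stated method and does not fill a gap.

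**Conclusion.** The point holds as a low-severity efficiency matter on a secondary outcome. The protocol fixes a comparison that is valid, and unbiased over randomisation, but which sets the baseline coefficient at 1 when the data to estimate it are collected for every implant.

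The size cannot be settled from the protocol. It runs from a variance reduction of about 40% (equal SDs, ρ = 0.2), through 25% (ρ = 0.5) and 15% (ρ = 0.7), to nothing, or a loss of about 2–3%, when the slope is near 1. Given subcrestal placement and a baseline film taken after grafting, the equal-SD figures are not to be taken as expected values. The case rests on a small, bounded cost set against a possibly useful gain, and on less dependence on whatever baseline difference occurs.

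**What to change.** In Statistical analysis, take marginal bone level out of the general t-test sentence and state, before unblinding:
- marginal bone level at 1 year and at 5 years is compared between arms by a linear model containing arm and that implant's baseline level (the mesial–distal mean);
- the adjusted difference is reported with its 95% confidence interval;
- the unadjusted t-test on change is shown as a supporting result.

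Add a note that the baseline film is taken after grafting, so a baseline difference between arms may partly reflect the material, and the two results should be read together.

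The cost is a sentence or two of wording and one degree of freedom. No new data or visits are needed, and the sample size does not change. The choice should be fixed in advance, because adjustment added after an imbalance has been seen would be post hoc.
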